11.3 Clinical laboratory evaluations

All laboratory results (clinical chemistry, hematology and urinalysis) outside the normal ranges will be listed by study participant, phase, treatment sequence, timepoint and parameter including most recent treatment received, changes from Baseline for numeric variables, the reference ranges and a flag to indicate whether values are below the lower limit of the reference range or above the upper limit of the reference range. The listing will include any laboratory value out of normal range at the timepoint it occurred only.

Separate listings of clinical chemistry and hematology laboratory results outside the normal ranges will be provided. These listings will include all data for a parameter for which a participant has at least one abnormal value during the study.

Urinalysis results will be listed by study participant, phase, treatment and timepoint including changes from Baseline for numeric variables, the reference ranges and flags for values outside the normal ranges.

A separate listing for laboratory results meeting the criteria for potential drug-induced liver injury (PDILI) will be provided. The listing will present the study participant who meets one or more of the following criteria for PDILI at any time point:

- Alanine aminotransferase (ALT) or aspartate aminotransferase (AST) $\geq 3x$ upper limit of normal (ULN)
- Alkaline phosphatase $\geq 2x$ ULN
- Total bilirubin increase $\geq 2x$ ULN

Clinical chemistry and hematology parameters will be summarized by phase, treatment and timepoint for both absolute values and changes from Baseline.

Laboratory variables will be grouped according to the laboratory function panel (Table 10-1) and categorized as normal, high or low, if applicable, based on the reference range supplied by the analytical laboratory. For selected variables that are identified in Table 10-1 the change in category from Baseline will be presented in shift table at all post-Baseline time points.

Any additional laboratory variables not included in the outputs described previously will be listed separately. These will include the following:

- Serology
- Alcohol breath test
- Serum pregnancy test (for women of childbearing potential)
- Urine toxicology screen

Figures of mean and mean change from Baseline may be presented for selected laboratory variables that will be identified at the DEM.

Table 11-1: Laboratory measurements

Laboratory Assessments	Parameters		
Hematology ¹	Platelet Count ²	RBC Indices:	WBC Count with
	RBC Count	MCV	Differential:
	Hemoglobin	MCH	Neutrophils ²
	Hematocrit	%Reticulocytes	Lymphocytes ² Monocytes Eosinophils Basophils

Laboratory Assessments	Parameters			
Clinical Chemistry ¹	Blood Urea Nitrogen ² (BUN)	Potassium	Aspartate Aminotransferase ² (AST)/Serum Glutamic-Oxaloacetic Transaminase (SGOT)	Total and direct bilirubin (direct is only measured if total >1xULN)
	Creatinine ²	Sodium	Alanine Aminotransferase ² (ALT)/Serum Glutamic-Pyruvic Transaminase (SGPT)	Total Protein
	Glucose (fasting at Screening)	Calcium	Alkaline phosphatase ² (ALP)	
Routine Urinalysis ¹	Specific gravity, pH, glucose, protein, blood, ketones, bilirubin, urobilinogen, nitrite, leukocyte by dipstick. If protein or blood or leukocytes are abnormal (positive), a microscopic examination of the sediment will be performed.			
Other Screening Tests	
 • Follicle-stimulating hormone (at Screening only to confirm postmenopausal status in female study participants) • Urine drug screen (to include at minimum: amphetamines, barbiturates, cocaine, opiates, cannabinoids and benzodiazepines) • Breath alcohol test • Pregnancy test: Urine or serum beta human chorionic gonadotropin (hCG) test (as needed for women of childbearing potential; serum hCG test used at Screening only) • Serology (HIV 1 and 2 Ab, HBsAg, HCV-Ab) 			

ALP=alkaline phosphatase; ALT=alanine aminotransferase; AST=aspartate aminotransferase; HBsAG=hepatitis B surface antigen; HCV-Ab=hepatitis C antibody; HIV-1/2Ab=human immunodeficiency virus-1/2 antibodies

¹ Hematology, clinical chemistry, and urinalysis assessments will be performed under fasting conditions at Screening and non-fasting conditions at all other assessments.

² Shift tables will be presented for these variables.

11.4 Vital signs, physical findings, and other observations related to safety

11.4.1 Vital signs

The following vital signs measurements will be assessed:

- Systolic and diastolic blood pressure
- Pulse rate

- Body temperature (aural)
- Respiratory rate

Vital signs measurements will be summarized and listed by phase, treatment sequence, position (standing (screening only) and supine) and timepoint including changes from Baseline and most recent treatment received. The listing will also include details to abnormal values. Vital signs with values below lower limit of normal and a decrease greater than the limit given in the following table or vital signs with values above upper limit of normal and an increase greater than the given value in the table will be classified as abnormal.

Table 11–2: Reference ranges for vital signs

Variable	Unit	Low ^a	High ^a
Systolic blood pressure	mmHg	Value <90 and/or ≥ 20 decrease from Baseline	Value >140 and/or ≥ 20 increase from Baseline
Diastolic blood pressure	mmHg	Value <50 and/or ≥ 15 decrease from Baseline	Value >90 and/or ≥ 15 increase from Baseline
Pulse rate	bpm	Value <45 and/or ≥ 15 decrease from Baseline	Value >90 and/or ≥ 15 increase from Baseline

11.4.2 Electrocardiogram

12-lead ECG will be recorded 3 times at each time point. The individual mean at each time point will be calculated as raw parameters for descriptive analysis. The individual mean and change from Baseline will be summarized using descriptive statistics by phase and treatment at each time point.

All standard 12-lead ECD recordings will be taken in triplicate with the study participant resting in the supine position for at least 5 minutes. The following ECG parameters will be reported:

- PR interval
- QT interval
- QRS interval
- QTc interval (QT corrected for heart rate using Fridericia’s formula [QTcF])
- Heart rate

The individual measurements and the mean of the triplicate measurements will be reported in the by- participant listings including change from Baseline and most recent treatment received and will be presented by phase, treatment sequence and timepoint.

Measured values and change from Baseline will be summarized by phase, treatment and ECG variable at each timepoint (based on the mean of the triplicate values at each timepoint). The mean change for ECG parameter will also be displayed graphically. Additionally, the following cut-points in QTcF (observed data and change from Baseline), based on the mean of the triplicate data, will be summarized categorically (number and percentage of participants) by treatment group at each timepoint. For observed data:

- <450 msec
- ≥ 450 to <480 msec

-
- ≥ 480 to < 500 msec
 - ≥ 500 msec

Absolute change from Baseline in QTcF:

- < 30 msec
- ≥ 30 to < 60 msec
- ≥ 60 msec

All ECG findings for the individual triplicate measurements will be listed separately. Any incomplete triplicate measurements at a given timepoint will be handled as described in [Section 4.2.3](#).

11.4.3 Other safety variable(s)

11.4.3.1 Physical examination

Study participants with abnormalities in the physical examination will be listed including details of the abnormality.

11.4.3.2 Columbia-Suicide Severity Rating Scale

Columbia-Suicide Severity Rating Scale (C-SSRS; Posner et al, 2011) data will be listed by treatment sequence. Module of the questionnaire, time point, question and the associated response will be listed for all the visit days where this questionnaire is collected.

12 OTHER ANALYSES

Not applicable.

14 APPENDICES

14.1 Appendix 1: VAS feeling high, internal and external perception (Bowdle)

The Bowdle Visual Analogue Scale (B-VAS) evaluates psychedelic effects (Bowdle et al, 1998). It consists of 13 100-mm self-rated visual analogue scales from which two composite scales are calculated: internal perception (six items) and external perception (5 items).

The individual items of the B-VAS are listed below:

1. My body or body parts seemed to change their shape or position
2. My surroundings seemed to change in size, depth, or shape
3. The passing of time was altered
4. I had feelings of unreality
5. It was difficult to control my thoughts
6. The intensity of colors changed
7. The intensity of sound changes
8. I heard voices or sounds that were not real
9. I had the idea that events, objects, or other people had particular meaning that was specific for me
10. I had suspicious ideas or the belief that others were against me
11. I felt anxious
12. I felt high
13. I felt drowsy

The two composite scales, internal perception and external perception, are calculated as follows (Zuurmann et al, 2008):

- External perception = $[\log_{10}(\text{Item1}+2) + \log_{10}(\text{Item2}+2) + \log_{10}(\text{Item3}+2) + \log_{10}(\text{Item5}+2) + \log_{10}(\text{Item6}+2) + \log_{10}(\text{Item7}+2)]/6$
- Internal perception = $[\log_{10}(\text{Item4}+2) + \log_{10}(\text{Item8}+2) + \log_{10}(\text{Item9}+2) + \log_{10}(\text{Item10}+2) + \log_{10}(\text{Item11}+2)]/5$

Item 12 is the individual VAS feeling high (no derivation is required).

14.2 Appendix 2: VAS Bond-Lader

The Bond-Lader VAS evaluates mood and alertness (Bond and Lader, 1974). It consists of 16 100-mm self-rated visual analogue scales (Figure 14-1) from which three factors are calculated: alertness, calmness, and contentment.

The three factors are calculated as follows:

- Alertness = (Item1 + Item3 + Item4 + Item5 + Item6 + Item9 + Item11 + Item12 + Item15)/9
- Calmness = (Item7 + Item8 + Item13 + Item14 + Item16)/5
- Contentment = (Item2 + Item10)/2

Certain scale scores may need to be inversed prior to calculation (Bond and Lader, 1974) based on the frequency distribution of the scales.

Figure 14-1: Bond-Lader VAS

1. Please rate the way you feel in terms of the dimensions given below.
2. Regard the line as representing the full range of each dimension.
3. Rate your feelings as they are at the moment.
4. Mark clearly and perpendicularly across each line.

	Scales				
Factor 1 (nine scales)	1. Alert	Drowsy
	11. Attentive	Dreamy
	6. Energetic	Lethargic
	4. Clear-headed	Muzzy
	5. Well-coordinated	Clumsy
	9. Quick-witted	Mentally slow
	3. Strong	Feeble
	15. Interested	Bored
	12. Proficient	Incompetent
Factor 2 (five scales)	13. Happy	Sad
	14. Amicable	Antagonistic
	8. Tranquil	Troubled
	7. Contented	Discontented
	16. Gregarious	Withdrawn
Factor 3 (two scales)	2. Calm	Excited
	10. Relaxed	Tense

Note: Scales not to size.

STATISTICAL ANALYSIS PLAN SIGNATURE PAGE

This document has been reviewed and approved per the Review and Approval of Clinical Documents Standard Operating Procedures. Signatures indicate that the final version of the SAP or amended SAP is released for execution.

This document cannot be used to support any marketing authorization application and any extensions or variations thereof.

REDACTED COPY

Approval Signatures

Name: UP0071-SAP
Version: 1.0
Document Number: CLIN-000139190
Title: UP0071-SAP
Approved Date: 28 Jan 2020

Document Approvals	
Approval Verdict: Approved	Name: [REDACTED] Capacity: Clinical Date of Signature: 28-Jan-2020 12:45:16 GMT+0000
Approval Verdict: Approved	Name: [REDACTED] Capacity: Clinical Date of Signature: 28-Jan-2020 17:06:30 GMT+0000

REDACTED COPY
This document cannot be used to support any marketing authorization application and any extensions or variations thereof.

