2 PROTOCOL SUMMARY

2.1 Study objectives and endpoints

2.1.1 Part A

Objectives	Endpoints
Primary	
To evaluate the PD interaction between steady-state treatment with PSL and ethanol	
 Smooth pursuit (%) to assess eye movement coordination and attention
Secondary	
To evaluate the PK interaction between steady-state treatment with PSL and ethanol	
 Ethanol dose infused over time $C_{max,ss}$ and AUC_{τ}, obtained from the plasma concentration-time profiles for PSL and its metabolites
To evaluate the PD interaction between steady-state treatment with PSL and ethanol	
 Saccadic peak velocity (degrees/sec) to assess sedation Adaptive tracking (%) to assess visuo-motor control and vigilance Body Sway to assess postural stability
To evaluate the safety and tolerability of PSL in study participants receiving concomitant ethanol	
 Adverse events (AEs), serious adverse events (SAEs), treatment-related AEs, and AEs leading to discontinuation of the study

Other	
To evaluate the safety and tolerability of PSL in study participants receiving concomitant ethanol	
 Vital signs (pulse rate, respiratory rate, systolic blood pressure [SBP], and diastolic blood pressure [DBP]) 12-lead electrocardiogram (ECG) parameters Physical examination findings Clinical laboratory test results (hematology, clinical chemistry, and urinalysis)
To evaluate the PD interaction between steady-state treatment with PSL and ethanol	
 Visual analogue scales (VAS) Bond & Lader to assess alertness, mood, and calmness VAS feeling high, internal and external perception (Bowdle) VAS for alcohol intoxication to assess the effects of ethanol
To evaluate the PK interaction between steady-state treatment with PSL and ethanol	
 t_{max} and C_{trough} obtained from the plasma concentration-time profiles for PSL and its metabolites
To collect and store blood for potential ADME genotype (if needed)	
 Possible ADME genotyping for drug metabolizing enzymes (depending on the outcome of PSL (and metabolite) PK analyses)
To collect urine samples for additional PK analyses depending on the outcome of PSL (and metabolite) PK analyses, if needed	
 Urine sample PK analysis

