2.1.2 Part B

Objectives	Endpoints
Primary	
To evaluate the PK interaction between steady-state treatment with PSL and CBD	
 $C_{max,ss}$ and AUC_{τ} obtained from the plasma concentration-time profiles for PSL and CBD
Secondary	
To evaluate the PK interaction between steady-state treatment with PSL and CBD	
 $t_{1/2}$, and $CL_{ss/F}$ obtained from the plasma concentration-time profiles for PSL and CBD
To evaluate the PD interaction between steady-state treatment with PSL and CBD	
 Smooth pursuit (%) to assess eye movement coordination and attention

	
 • Saccadic peak velocity (degrees/sec) to assess sedation • Adaptive tracking (%) to assess visuo-motor control and vigilance • Body Sway to assess postural stability
To evaluate the safety and tolerability of PSL in study participants receiving concomitant CBD	
 • Adverse events (AEs), serious adverse events (SAEs), treatment-related AEs, and AEs leading to discontinuation of the study
Other	
To evaluate the safety and tolerability of PSL in study participants receiving concomitant CBD	
 • Vital signs (pulse rate, respiratory rate, systolic blood pressure [SBP], and diastolic blood pressure [DBP]) • 12-lead electrocardiogram (ECG) parameters • Physical examination findings • Clinical laboratory test results (hematology, clinical chemistry, and urinalysis)
To evaluate the PD interaction between steady-state treatment with PSL and CBD	
 • Visual analogue scales (VAS) Bond & Lader to assess study participant alertness, mood, and calmness • VAS feeling high, internal and external perception (Bowdle)
To evaluate the PK interaction between steady-state treatment with PSL and CBD	
 • t_{max} and C_{trough} obtained from the plasma concentration-time profiles for PSL and CBD • $C_{max,ss}$, AUC_{τ}, $t_{1/2}$, t_{max}, and metabolite/parent ratio (based on $C_{max,ss}$ and AUC_{τ}) obtained from the plasma concentration-time profiles for PSL metabolites and CBD active metabolite
To evaluate the plasma PK of single dose of CBD (Treatment Period 1)	
 • C_{max}, AUC_{0-t}, AUC, t_{max}, $t_{1/2}$ and CL/F

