10 PHARMACODYNAMICS

Pharmacodynamic parameters (absolute values and change from Baseline) will be summarized by phase, treatment, phase day and timepoint using the FAS. Figures of summaries and individual assessments will be based on the FAS.

The PD parameters include:

- Smooth Pursuit Eye Movements
- Body Sway
- VAS Mood and Alertness (Bond & Lader)
- VAS feeling high, internal and external perception (Bowdle)
- Saccadic eye movements
- Adaptive tracking
- VAS alcohol intoxication (Part A only)

For the derivation of VAS feeling high, internal and external perception (Bowdle) and VAS Mood and Alertness (Bond & Lader) see [Appendix 14.1](#) and [Appendix 14.2](#) respectively. The raw values of VAS alcohol intoxication will be presented, and any derivation required will be outlined in CSR.

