10.1.2 Statistical analysis of pharmacodynamics variables

For the analysis of PD variables, there will be two baselines per study participant (Kenward-Rogers, 2010):

1. Between subject baseline = mean of all predose PD parameter for each subject
2. Within subject baseline = baseline at given day – between subject baseline

The PD parameters will be analyzed separately by a repeated measures ANOVA with treatment, time, treatment by time, period and sequence as fixed effects; time as repeated measure; with subject by period and subject as random effects and within subject baseline and between subject baseline and the baseline interactions with time as covariates. [Section 10.1.2.1](#) and [Section 10.1.2.2](#) specify which treatments to include in the model.

Due to the confounding of treatment within period within the design only the periods of interest will be included in any given comparison. For example, if the comparison is within the interaction phase then only Periods 4 and 5 will be kept in the model.

Period should be removed from the model statement due to confounding with treatment in any comparisons where either test or reference period only contains one treatment option. It will be left in the repeated statement as period is synonymous with treatment.

The following SAS code may be used for the repeated measures ANOVA stated above:

Contrasts for each PD variable will be reported along with 95% CI. Variables will initially be analyzed without transformation, but if visual inspection of the residual plots suggest otherwise (data are not normally distributed), an appropriate transformation may be applied.

Further exploratory analyses for PD variables may be conducted by UCB.

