10.1.2.1 Ethanol and PSL (Part A)

The similarity of PD parameters between treatments will be analyzed using the model specified in [Section 10.1.2](#), where treatment includes Ethanol, Placebo, PSL+Ethanol and PSL+ Placebo.

The following contrasts will be calculated within the model:

- PSL+Ethanol (Treatment Period 4/5: Day 5/7) vs PSL+Placebo (Treatment Period 4/5: Day 5/7) (primary comparison)
- PSL+Placebo (Treatment Period 4/5: Day 5/7) vs Placebo (Treatment Period 1/2: Day 1)
- Ethanol (Treatment Period 1/2: Day 1) vs Placebo (Treatment Period 1/2: Day 1)
- PSL+Ethanol (Treatment Period 4/5: Day 5/7) vs Ethanol (Treatment Period 1/2: Day 1)

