10.1.2.2 CBD and PSL (Part B)

The similarity of the PD parameters between treatment will be analyzed using the model specified in [Section 10.1.2](#), where treatment includes CBD, PSL, CBD+PSL and CBD+Placebo.

The following contrasts will be calculated within the model:

- CBD+PSL (Treatment Period 4/5: Day 5) vs PSL (Treatment Period 2: Day 5) (primary comparison)
- CBD+PSL (Treatment Period 4/5: Day 5) vs CBD (Treatment Period 3: Day 16)
- CBD+PSL (Treatment Period 4/5: Day 5) vs CBD+Placebo (Treatment Period 4/5: Day 5)

This analysis will also be performed for PD variables measured in Treatment Period 4/5, Day 1. Any treatment effect may be compounded by time in the first and second comparison stated above. Additionally, there may be a learning effect due to study participants performing the PD assessments multiple times.

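### SAP Appendix 14.2 gives the Bond-Lader Calmness and Contentment factors each other's name

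*SAP*

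**What the plan says.** SAP Section 10 sends the programmer to the appendices for scoring: "For the derivation of VAS feeling high, internal and external perception (Bowdle) and VAS Mood and Alertness (Bond & Lader) see" Appendices 14.1 and 14.2. Appendix 14.2 gives three formulas. Alertness is the mean of nine items (1, 3, 4, 5, 6, 9, 11, 12, 15). The other two are "Calmness = (Item7 + Item8 + Item13 + Item14 + Item16)/5" and "Contentment = (Item2 + Item10)/2".

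Figure 14-1, in the same appendix, prints the anchors of all 16 scales in three blocks, labelled only Factor 1 (nine scales), Factor 2 (five) and Factor 3 (two).

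The SAP endpoint tables place Bond-Lader among the 'Other' PD endpoints: "Visual analogue scales (VAS) Bond & Lader to assess alertness, mood, and calmness" in Part A (Section 2.1.1) and "Visual analogue scales (VAS) Bond & Lader to assess study participant alertness, mood, and calmness" in Part B (Section 2.1.2). Protocol Section 8.7.3 names the three factors as alertness, calmness and contentment but does not say which items belong to which.

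For analysis, SAP Section 10.1.2 states: "Contrasts for each PD variable will be reported along with 95% CI". Sections 10.1.2.1 and 10.1.2.2 then list the comparisons for each Part.

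**The concern.** The scale anchored Calm is left out of Calmness, and the scale anchored Contented is left out of Contentment. The items point to a simple exchange of names between the two factors.

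Programmed as written, the Calmness and Contentment summaries, LS-mean plots, contrasts and confidence intervals in both Parts would each carry the other factor's name. A reader asking whether padsevonil with ethanol or with CBD alters calmness would be shown a score built from Happy, Amicable, Tranquil, Contented and Gregarious. The Calm/Relaxed score would appear as contentment.

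The error would be hard to see in the output. Both formulas run and return plausible values on the 0 to 100 mm range, so range and missing-data checks would pass. SAP Section 4.3 also assigns the PD programming to teams independent of the study team, so the written specification carries more weight than usual.

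**Working it through.** The documents give no figure to reproduce. The check compares the formulas with the item list in the same appendix.

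**Step 1: do the formulas match the blocks in Figure 14-1?**

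| SAP name | Items in formula | Left-hand anchors in Figure 14-1 | Block |
|---|---|---|---|
| Alertness | 1, 3, 4, 5, 6, 9, 11, 12, 15 | Alert, Strong, Clear-headed, Well-coordinated, Energetic, Quick-witted, Attentive, Proficient, Interested | Factor 1 (9) |
| Calmness | 7, 8, 13, 14, 16 | Contented, Tranquil, Happy, Amicable, Gregarious | Factor 2 (5) |
| Contentment | 2, 10 | Calm, Relaxed | Factor 3 (2) |

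Each formula reproduces one block exactly. 9 + 5 + 2 = 16, every item is used once, and the divisors 9, 5 and 2 are right. Grouping and arithmetic are sound.

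**Step 2: do the names match the items?**

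- Contentment: 0 of 2 items fit the name. Both are calm/tension scales.
- Calmness: 1 of 5 items fits (item 8, Tranquil). The block includes Contented and Happy.
- With the two names exchanged, both Calm and Relaxed fall under Calmness, and Contented and Happy fall under Contentment.

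**Step 3: what would be reported?** As an illustration with assumed scores, put all items at 50 mm and then move only items 2 and 10 to 70 mm.

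- SAP Calmness = (50 + 50 + 50 + 50 + 50)/5 = 50, a change of 0.
- SAP Contentment = (70 + 70)/2 = 70, a change of +20.

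A shift confined to the Calm and Relaxed scales is reported wholly as a change in contentment.

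**Step 4: how many results carry the wrong name?** Section 10.1.2.1 lists 4 comparisons for Part A and Section 10.1.2.2 lists 3 for Part B. Assuming one contrast per listed comparison per factor:

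- Per factor: 4 + 3 = 7. Three factors: 3 × 7 = 21. Two misnamed factors: 2 × 7 = 14.
- Section 10.1.2.2 adds: "This analysis will also be performed for PD variables measured in Treatment Period 4/5, Day 1". That is up to 3 more per factor, so up to 21 + 9 = 30 in total and 14 + 6 = 20 misnamed.
- The share is 2/3 either way (14/21 = 20/30).

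The numerical change to any estimate or interval is 0.

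**The case against.** The strongest reply is that Figure 14-1 does not name its factors. The authoritative names belong to the instrument's source publication, which was not available here, so the argument rests on item wording, and Tranquil does fit the name the SAP gives its block. That is a fair statement of the evidence, but it does not rescue the assignment. One item in five cannot explain why Calm and Relaxed, and nothing else, should define Contentment. Nothing elsewhere in either document supports the printed mapping. Protocol Section 8.7.3 lists the names in the same order as the SAP formulas, which may show how the labels came to be attached to Factors 1, 2 and 3, but it gives no item mapping. For the same reason, the absence of an entry in SAP Section 3.9 (changes to protocol-defined analyses) proves nothing either way.

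Four further points stand in whole or in part:

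- This is a labelling error. No computed value is wrong, and anyone holding the SAP could recover the right score from the printed formulas.
- The contrast counts depend on one contrast per comparison. The model includes treatment by time, and the text does not say whether contrasts are overall, by timepoint or both. The statement free of that assumption is 2 of 3 factors.
- Bond-Lader is an 'Other' endpoint. The primary and secondary endpoints, the sample size and the safety analyses are untouched.
- Exchanging the names alone leaves a loose end. The endpoint tables say mood where the appendix says contentment.

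These limit the weight of the point and add to the fix. They do not remove the contradiction.

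**Conclusion.** The point holds. Appendix 14.2 contradicts its own item list: the names Calmness and Contentment are exchanged, and Section 10 makes that appendix the derivation to be used. If it is followed as written, 2 of the 3 Bond-Lader factors are reported under the wrong name in both Parts. This rests on the wording of the scales in Figure 14-1, which is unambiguous for items 2, 7 and 10, and on the formulas being programmed as printed. It should be corrected because calmness is a named endpoint, but it bears on interpretation of an 'Other' PD endpoint and not on the trial's main conclusions.

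**What to change.** In Appendix 14.2, and in the derivation code and variable labels, write:

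- Calmness = (Item2 + Item10)/2
- Contentment = (Item7 + Item8 + Item13 + Item14 + Item16)/5

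Leave Alertness unchanged. In the same edit, use one term, mood or contentment, for the five-item score in both the endpoint tables and the appendix.

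The cost is two exchanged labels and one wording alignment. SAP Section 1 calls for a SAP amendment when analysis definitions are modified before database lock, so the change is best made then, ahead of table production.

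A lesser item could be settled at the same time. Appendix 14.2 says some scales may need inverting, on the basis of their score distributions, and does not say which. A short list of item directions, taken from the anchors of the computerized form actually administered and fixed before unblinding, would remove that discretion. The documents do not show that the present rule would reverse a sign, so this is a tidying step and not part of the error.

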8.7.3 VAS according to Bond-Lader

The study participative VASs for this study are the Bond and Lader of Mood and Alertness Scales (Bond and Lader, 1974). This VAS scale consists of 16 bipolar self-rating 100mm long lines between 2 opposite adjectives. The study participant will indicate on the line how she/he is feeling at the evaluation time. The response is scored by measuring the distance in mm between the left end of the line and the study participant’s mark. This questionnaire derives 3 factors that assess change in self-rated alertness, self-rated calmness, and self-rated contentment. A computerized version of this test will be used, with the participant using the computer mouse.

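### Bond-Lader items should be oriented by their printed poles, not inverted by their frequency distribution; the meaning of a high score and two factor labels also need fixing

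*SAP*

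**What the plan says.** Protocol 8.7.3 describes 16 bipolar 100 mm lines, completed on a computer. Each response is "scored by measuring the distance in mm between the left end of the line" to the participant's mark. On the purpose, the same section says: "This questionnaire derives 3 factors that assess change in self-rated alertness, self-rated calmness, and self-rated contentment".

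SAP section 10 sends the derivation to Appendix 14.2, which gives three unsigned means:

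- "Alertness = (Item1 + Item3 + Item4 + Item5 + Item6 + Item9 + Item11 + Item12 + Item15)/9"
- "Calmness = (Item7 + Item8 + Item13 + Item14 + Item16)/5"
- "Contentment = (Item2 + Item10)/2"

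The only statement on direction follows: "Certain scale scores may need to be inversed prior to calculation (Bond and Lader, 1974) based on the frequency distribution of the scales". Figure 14-1 then lists the items by factor with a left and a right adjective, for example "1. Alert Drowsy". Neither document says whether a high factor score means more or less of the named quality.

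The objectives tables of both documents place Bond-Lader in the Other tier for Part A and Part B.

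**The concern.** Whether an item has to be reversed before averaging depends on its wording: which adjective is on the left and which on the right. This is known once the computerized form is built, before anyone has answered it. A frequency distribution shows where marks fall. It does not show which end of the line is the alert one.

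The SAP therefore states a rule with the wrong criterion and leaves its application open: the items are unnamed, inversion is optional, and there is no threshold. Two programmers following Appendix 14.2 could invert different items and obtain different sizes, or opposite signs, for the same contrast in SAP 10.1.2.1 or 10.1.2.2. With no stated meaning for a high score, a reader of the tables would naturally take a rise in Alertness as less sedation, and on the Figure 14-1 layout with no inversion it would mean more.

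**Working it through.** The plan gives no figure to reproduce. The check takes the scoring rule as written and follows a common shift through it.

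**Inputs**

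- Scoring origin: mm from the left end (Protocol 8.7.3).
- Poles: in SAP Figure 14-1 the favourable adjective is on the left for all 16 items.
- Factors: unsigned means of 9, 5 and 2 items (SAP 14.2). The item sets add to 9 + 5 + 2 = 16, each item is used once, and the divisors match.
- Assumed for illustration, since the documents give no values: every item starts at 30 mm and moves 20 mm to the right, towards the unfavourable pole.

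**Formula.** Inverting an item replaces x by 100 − x, so a shift of +d becomes −d. If all m items of a factor shift by d and k of them are inverted, then

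change in factor = [(m − k)d − kd]/m = d(m − 2k)/m.

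The multiplier (m − 2k)/m depends on neither the assumed baseline nor the assumed shift.

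**Alertness, m = 9, d = +20 mm towards the drowsy end**

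| Items inverted (k) | Multiplier | Change in score |
|---|---|---|
| 0 | 1.00 | +20.0 |
| 1 | 0.78 | +15.6 |
| 2 | 0.56 | +11.1 |
| 3 | 0.33 | +6.7 |
| 4 | 0.11 | +2.2 |
| 5 | −0.11 | −2.2 |
| 6 | −0.33 | −6.7 |
| 7 | −0.56 | −11.1 |
| 8 | −0.78 | −15.6 |
| 9 | −1.00 | −20.0 |

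With k = 0 the mean goes from 30 to 50: the full size, but Alertness has risen in a drowsier participant. With k = 9 it goes from 70 to 50: the full size in the direction of the name. Every k in between shrinks the effect. Nine is odd, so a common shift never vanishes entirely here; at least 1/9 of it remains.

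**The other two factors.** For five items the multipliers are 1, 0.6, 0.2, −0.2, −0.6 and −1. For two items they are 1, 0 and −1, so inverting one of the two cancels a common shift exactly.

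**Labels.** Matching the formulas to Figure 14-1:

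| SAP factor name | Items | Left-hand adjectives in Figure 14-1 |
|---|---|---|
| Calmness | 7, 8, 13, 14, 16 | Contented, Tranquil, Happy, Amicable, Gregarious |
| Contentment | 2, 10 | Calm, Relaxed |

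Calm and Relaxed form the factor called Contentment, while Contented and Happy sit in the one called Calmness. On the SAP's own wording the two names look interchanged. Fixing the item direction alone would leave both factors misnamed.

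**The case against.** Several points on the other side stand.

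- **The on-screen form is not shown.** Figure 14-1 groups items by factor and participants used a computerized version, so its left-right layout may differ. If some poles were swapped on screen, inverting those items would be correct and necessary. That is still a decision from the printed poles, so it does not rescue the frequency criterion.
- **The cited scale paper may name the items.** That cannot be checked here. What can be said is that the SAP does not reproduce such a list and gives the distribution as its basis.
- **Uniform left-end scoring is not a bias.** On the untransformed scale it gives the same absolute estimates and interval widths with the sign reversed. It is acceptable if the direction is stated.
- **The partial-inversion figures are hypothetical.** No passage says how many items would be inverted. The multipliers show what the rule permits and do not estimate an effect in this trial.

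Two stronger readings are tempting. A reader might infer that Alertness must either run backwards or have its item effects cancel. The documents do not support that: inverting every item in a factor is also open under the SAP and gives the correct score, and for nine items with a common shift, partial inversion attenuates or reverses the change but never removes it. A reader might also infer that sedating treatments would steer the inversion and so bias the comparison between treatments. The SAP sentence concerns scale scores and reads most naturally as one decision per item across all records; nothing in it suggests inversion by treatment.

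**Conclusion.** The point holds as a defect in the scoring rule. SAP 14.2 bases item inversion on the data when the printed poles determine it, does not say which items are affected, and does not define a high score. On the documented layout, no inversion gives the right size with a sign opposite to the factor name. Inverting some but not all items of a factor multiplies a common shift by (m − 2k)/m, which is exactly zero for one of two items. Only whole-factor inversion gives the full effect in the named direction. Separately, the Calmness and Contentment labels appear swapped.

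This rests on Figure 14-1 matching the administered form and, for the multipliers, on equal shifts across the items of a factor.

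The consequence is limited. Bond-Lader is an Other endpoint in both parts; the Part A primary endpoint (smooth pursuit) and the PK analyses do not use it. Sedation is also assessed by saccadic peak velocity, a secondary endpoint whose direction Protocol 8.7.4 states. It would be wrong to conclude that the trial's main assessment of sedation or of the interaction is compromised.

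**What to change.** In SAP Appendix 14.2, before unblinding:

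1. Delete the frequency-distribution sentence.
2. Orient every item by the printed poles of the administered version, so that all items in a factor run the same way. If that version matches Figure 14-1, use either 100 minus the distance from the left for all 16 items, or the distance from the left for all 16. List any item whose poles differ on screen and reverse it by name.
3. State in the SAP and in the table footnotes what a higher score means for each factor.
4. Reconcile the Calmness and Contentment names with items 7, 8, 13, 14, 16 and items 2, 10.

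The cost is appendix wording, a check of the on-screen form, a line of derivation code and corrected labels. No new data are needed, and no other analysis changes.
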